- QTcF interval ≥ 501 msec and > 60 msec prolongation from baseline (defined as the average QTcF value from pre-dose C1D1 ECGs), or associated with Torsades de pointes, polymorphic ventricular tachycardia, or serious arrhythmia
- Prolonged delay (> 2 weeks) in initiating Cycle 2 due to treatment-related toxicity;
- Any treatment-related toxicity that causes the subject to discontinue treatment during Cycle 1
- Any Grade 5 toxicity.

Duration of Treatment

Subjects may continue to receive study therapy until the earliest of the following: subject withdrawal from study, confirmed progression of cancer, intolerable study-drug-related toxicity despite appropriate dose modification, the development of intercurrent illness that precludes continued study therapy, pregnancy or breastfeeding, substantial noncompliance with study procedures, completion of Treatment Phase comprising up to 35 treatment cycles for FLX475, or study discontinuation by Sponsor.

Study Endpoints:

Efficacy:

The primary efficacy endpoint of the study is objective response rate (ORR), defined as the proportion of subjects who have best overall response of CR or PR as determined using RECIST 1.1 ([Appendix 4](#)) for subjects with melanoma.

Other efficacy endpoints are as follows:

- Overall Survival (OS), defined as the time from the date of start of treatment to the date of death from any cause. Subjects who are lost to follow-up and those who are alive at the date of data cutoff will be censored at the date the subject was last known alive, or date of data cutoff, whichever occurs first.
- Clinical Benefit Rate (CBR), defined as the proportion of subjects who achieve a CR, a PR, or durable SD duration of at least 6 months from start of study treatment.
- Time to Response, defined as the interval from start of study treatment to the first documentation of CR or PR.
- Duration of Response, defined as the interval from the first documentation of CR or PR to the earlier of the first documentation of PD or death from any cause.
- Progression-free Survival (PFS), defined as the interval from the start of study treatment to the earlier of the first documentation of PD or death from any cause.

Safety:

The primary safety endpoint in the safety run-in portion of the study is safety and tolerability by the determination of AEs, including DLTs. The following safety parameters will be characterized and summarized:

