As part of a safety run-in, the first six subjects on study will be treated with both the recommended Phase 2 dose of FLX475 (100 mg PO QD) and the approved dose of ipilimumab (3 mg/kg IV) and observed for a minimum of one cycle of treatment (21 days) for any unacceptable toxicities (dose-limiting toxicities or DLTs as described in [Section 10.4](#)) prior to enrolling additional subjects. A DLT can be observed in no more than one of the first six subjects during the first cycle of treatment before enrollment of the remainder of the study subjects can continue. If a treatment-related DLT is observed during the first cycle of treatment in more than one of the first six (or fewer) subjects, dose modification of either or both drugs will be considered by the Safety Review Committee prior to continuing enrollment, potentially in an additional safety run-in.

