Any subjects in the safety run-in phase who do not receive at least 80% of planned doses in Cycle 1 due to reasons other than DLT, or who stop treatment prior to completing evaluation for the initial 3 weeks of therapy (DLT Observation Period) due to PD or refusal to participate further for reasons other than DLT, will be replaced at that dose level to permit full evaluation of the safety run-in. See [Section 10.4](#) for the definition of a DLT.

9.1.4 *Removal of Subjects from Therapy or Assessment*

Discontinuation of study treatment does not represent withdrawal from the study.

The investigator may discontinue treating a subject with study treatment or withdraw the subject from the study at any time for safety or administrative reasons, but should inform or discuss with the Sponsor's medical monitor prior to doing so (when feasible). The subject may decide to discontinue study treatment or withdraw from the study at any time for any reason.

The reason for discontinuation of FLX475, ipilimumab, or both will be documented. If a subject discontinues study treatment, the subject will enter the Follow-Up Phase and complete protocol-specified End-of-Treatment and Follow-up visits, procedures, and survival follow-up, unless the subject withdraws consent. The investigator should confirm whether a subject will discontinue study treatment but agree to continue protocol-specified, post-treatment study visits, procedures, and survival follow-up, or whether the subject withdraws consent or is lost to follow-up. If a subject withdraws consent, the date will be documented in the source documents. The investigator, or designee, will complete the appropriate eCRF, indicating the primary reason for discontinuation. In addition, the date of final dose of study treatment(s) will be recorded on the appropriate eCRF.

All subjects who discontinue study treatment without having PD will continue to undergo tumor assessments using the same imaging schedule used during the Treatment Phase (i.e., every 9 weeks [± 1 week] in Year 1 or every 12 weeks [± 1 week] beyond Year 1) until the start of a new anticancer treatment, disease progression, pregnancy, or the end of the study, whichever occurs first, unless the subject withdraws consent, is lost to follow-up, or dies.

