12.1.2.1 Study Endpoints

12.1.2.1.1 Safety Endpoints

The primary safety endpoint of the study is safety and tolerability by the determination of AEs, including DLTs. The following safety parameters will be characterized and summarized:

- Treatment-emergent adverse events (TEAEs) and SAEs together with all other safety parameters
- Number (%) of subjects who discontinue treatment due to TEAEs
- Time to treatment failure due to toxicity, defined as the time from the date of start of treatment to the date that a subject discontinues study treatment due to TEAEs
- Dose-limiting toxicity (defined in [Section 10.4](#))
- Laboratory abnormalities
- Vital sign abnormalities
- Adverse ECG findings

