12.1.7.2 Pharmacodynamic, Pharmacogenomic, and Other Biomarker Analyses

Soluble, tissue, genetic and/or imaging biomarkers (baseline and/or posttreatment) may be summarized using descriptive statistics and correlated with clinical outcomes-related endpoints for safety and/or efficacy (including OR, PFS and OS) as appropriate. Changes from baseline in PD markers will be analyzed using appropriate methods if done. Details may be included in a separate analysis plan.

The effect of FLX475 in combination with ipilimumab on soluble, tissue, genetic and/or imaging biomarkers may be summarized using descriptive statistics based on the PK/PD analysis set. Pharmacokinetic/pharmacodynamic relationships (i.e., exposure-efficacy, and exposure-safety and exposure-biomarker relationships) will be modeled, if possible, using a mechanistic approach for effects of study treatment. Efficacy endpoints will include the primary endpoint of ORR and other efficacy-related metrics including but not limited to PFS (based on iRECIST) and OS. Safety endpoints will be the most frequent AEs of special interest and dose reductions. Exploratory/graphical analyses will be conducted for PK/PD evaluations, and, if possible, will be followed by model-based analyses.

The PK (and PK/PD, if done) analyses will be detailed in a separate analysis plan that will be provided at a later date and the result will be provided in a standalone report.

12.1.8 *Safety Analyses*

Safety analyses will be based on the Safety Analysis Set and summarized. Adverse events and SAEs, laboratory test results, vital signs, and ECG results will be summarized. Safety data will be summarized using descriptive statistics. Categorical variables will be summarized by number and percentage. Continuous variables will be summarized using n (number of subjects with available data), mean, standard deviation, median, first and third quartile, and range (minimum and maximum) unless otherwise specified. The type, frequency, severity, timing of onset, duration, and relationship to study treatments of any TEAEs, DLTs, SAEs, or AEs leading to discontinuation or dose modification (reduction/interruption) of either study treatment (FLX475 or ipilimumab); laboratory abnormalities; vital sign abnormalities; and adverse ECG findings will be analyzed.

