Data collected at unscheduled visits will not be included in by-visit summaries, but will be considered when endpoint derivations potentially include multiple visits (e.g., determination of baseline value, determination of worst post-baseline value, etc.). All data will be included in subject listings.

7.1.3 *Data Handling Rules*

Unless otherwise noted, values reported as greater than or less than some quantifiable limit (e.g., “< 1.0”) will be summarized with the sign suppressed in summary tables and

figures, using the numeric value reported. Data will display on subject listings to include the sign.

7.1.4 *Standard Calculations*

Where appropriate, the calculated study day of each assessment or event will be presented with the assessment or event date on subject data listings, where study day will be determined as:

- The assessment/event date minus the date of first dose of study drug, if the assessment/event date is prior to the date of first dose; and
- The assessment/event date minus the date of first dose of study drug, plus one, if the assessment/event date is on or after the date of first dose.

Other variables requiring calculations will be derived using the following formulas:

- **Days:** A duration between two dates expressed in days will be calculated using the following conventions:
 - Later date – earlier date + 1, if the earlier date is on or after the date of first dose of study drug; or
 - Later date – earlier date, if the earlier date is prior to the date of first dose of study drug.
- **Months:** A duration expressed in months will be calculated by dividing the duration in days by (365.25 / 12);
- **Years:** A duration expressed in years will be calculated by dividing the duration in days by 365.25;
- **Change from Baseline:** Change from baseline will be calculated as the post-baseline value minus the baseline value;
- **Percentage Change from Baseline:** Percentage change from baseline will be calculated as the change from baseline divided by the baseline value, multiplied by 100.

7.2 *Analysis Populations*

The analysis populations are defined as follows:

- **Full Analysis Set:** All subjects enrolled in the study, also known as the “Intent-to-Treat” (ITT) population.

- **Safety Analysis Set:** All subjects who receive at least one dose of the investigational product, FLX475 (even a partial dose).

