7.5.2 Adverse Events

All subjects will be assessed regularly for the potential occurrence of adverse events (AEs) from the date of informed consent to 90 days after the last dose of study treatment. The incidence of treatment-emergent adverse events (TEAEs) will be summarized and tabulated using Medical Dictionary for Regulatory Activities (MedDRA), by System Organ Class (SOC) and Preferred Term (PT). A TEAE is defined as an AE that first occurs or worsens in severity on or after the first dose of FLX475. All adverse events recorded in the eCRF will be presented in data listings.

The National Cancer Institute (NCI)/CTCAE v5.0 will be used to grade both clinical and laboratory AEs. A subject with several occurrences of the same AE will be counted once

and classified by the most severe occurrence. AEs with missing severity ratings will be classified as having unknown severity, but will be assigned Grade 3 severity for analysis and summarization.

The relationship of each AE to the study treatment will be classified as related or unrelated; an AE that is possibly, probably or definitely related to study treatment will be considered related. Any AE with an eCRF description of related will be considered related. A subject with several occurrences of the same AE will be counted once and classified as related if at least one of them is classified as related. An AE with a missing relationship to study treatment will be assumed to be related to study treatment for the purpose of analysis and summarization. Relationship of AEs to FLX475 and ipilimumab will be separately recorded and analyzed.

An overview of adverse events for the Safety Analysis Set will be provided, summarizing the incidence of the following:

- Any DLT;
- Any TEAEs; FLX475-related TEAEs; ipilimumab-related TEAEs;
- Any NCI/CTCAE Grade ≥ 3 TEAEs; FLX475-related NCI/CTCAE Grade ≥ 3 TEAEs; ipilimumab-related NCI/CTCAE Grade ≥ 3 TEAEs;
- Any serious TEAEs; FLX475-related serious TEAEs; ipilimumab-related serious TEAEs;
- Any discontinuation of study treatment due to TEAEs; discontinuation of FLX475 due to FLX475-related TEAEs; discontinuation of ipilimumab due to ipilimumab-related TEAEs;
- Any NCI/CTCAE Grade 5 TEAEs; FLX475-related NCI/CTCAE Grade 5 TEAEs; ipilimumab-related NCI/CTCAE Grade 5 TEAEs.

TEAE summaries by SOC and PT will be provided for the following:

- TEAEs (overall and FLX475 or ipilimumab related);
- Grade ≥ 3 TEAEs (overall and FLX475 or ipilimumab related);

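### DLT incidence is tabulated only on the Safety Analysis Set, so no planned table shows the run-in rate that matches the 1-of-6 rule

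*SAP*

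**What the plan says.** - **Table population.** SAP 7.5.2: "An overview of adverse events for the Safety Analysis Set will be provided, summarizing the incidence of the following". Any DLT is the first entry in the list that follows.
- **Who is in that population.** SAP 7.2: "All subjects who receive at least one dose of the investigational product, FLX475 (even a partial dose"). The only other set in SAP 7.2 is the Full Analysis Set. Protocol 12.1.2.3 defines more sets, but none for DLT evaluability. Protocol 12.1.8 uses the same population as the SAP and names DLTs among the safety data: "Safety analyses will be based on the Safety Analysis Set and summarized".
- **Who is replaced.** Protocol 9.1.3 replaces run-in subjects "who do not receive at least 80% of planned doses in Cycle 1 due to reasons other than DLT", and those "who stop treatment prior to completing evaluation for the initial 3 weeks of therapy (DLT Observation Period) due to PD" or through refusal for non-DLT reasons.
- **The run-in rule.** Protocol 6.2: "A DLT can be observed in no more than one of the first six subjects during the first cycle of treatment" if enrolment is to go on. Protocol 10.2.1 gives more than 1 of 6 as its example of an unacceptable result.
- **The endpoint.** The protocol synopsis says: "The primary safety endpoint in the safety run-in portion of the study is safety and tolerability by the determination of AEs, including DLTs". Protocol 12.1.2.1.1 words it for the whole study: "The primary safety endpoint of the study is safety and tolerability by the determination of AEs, including DLTs".

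**The concern.** The run-in is judged on six subjects with an adequate Cycle 1, and the replacement rule exists to secure those six. The SAP table uses a different denominator: everyone dosed, whether or not they could be assessed for a DLT and whether or not they belonged to the run-in. A reader of the study report would look for x of 6 and find x over some other number.

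SAP 7.7 drops the efficacy summaries because the study stopped early. Safety and tolerability is then the only primary objective that the SAP still summarises, and the DLT rate is its most decision-relevant figure. This sponsor has used the narrower denominator before: protocol 6.1.3.2.2 gives the DLT result of the pembrolizumab combination cohorts among DLT-evaluable subjects.

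**Working it through.** **Inputs.** Run-in size 6 and planned total 20 (SAP 7.6), which leaves 20 − 6 = 14 later subjects. The rule is at most 1 DLT in 6 (protocol 6.2). The numbers treated, replaced and with a DLT are not in the documents, so r, k and the 14 later subjects below are assumptions shown as ranges.

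**The plan's own figure.** The documents state no DLT rate, error rate or power. The rule implies that 1/6 = 16.7% passes and 2/6 = 33.3% does not.

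**Step 1: replaced subjects.** Replacement is for reasons other than DLT, so a replaced subject who took FLX475 adds 1 to the denominator and 0 to the numerator. With x DLTs and r replaced subjects, the run-in proportion becomes x/(6+r), that is (x/6) × 6/(6+r).

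| r | factor 6/(6+r) | x = 1 | x = 2 |
|---|---|---|---|
| 0 | 1.000 | 1/6 = 16.7% | 2/6 = 33.3% |
| 1 | 0.857 | 1/7 = 14.3% | 2/7 = 28.6% |
| 2 | 0.750 | 1/8 = 12.5% | 2/8 = 25.0% |
| 3 | 0.667 | 1/9 = 11.1% | 2/9 = 22.2% |

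The direction is fixed: the rate can only fall, or stay the same if r = 0.

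**Step 2: subjects enrolled after the run-in.** The DLT definition in protocol 10.4 covers Days 1–21 of Cycle 1 and is not limited to run-in subjects. Protocol 10.5.1 speaks of DLT assessment continuing in both parts of the study. Later subjects may therefore add to the numerator. With k DLTs among 14 later subjects and r = 0, the pooled rate is (x+k)/20.

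| k | x = 1 (run-in 16.7%) | x = 2 (run-in 33.3%) |
|---|---|---|
| 0 | 1/20 = 5.0% | 2/20 = 10.0% |
| 3 | 4/20 = 20.0% | 5/20 = 25.0% |
| 5 | 6/20 = 30.0% | 7/20 = 35.0% |

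The pooled rate reaches the run-in rate when (x+k)/20 ≥ x/6, or k ≥ 14x/6. That is 3 later DLTs for x = 1 (14/6 = 2.3) and 5 for x = 2 (28/6 = 4.7). Here the direction is not fixed.

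**Step 3: does another provision supply the figure?** SAP 7.1.1 splits tables by treatment group, not by run-in against later enrolment. Its default denominator, subjects with data available, does not settle the matter because DLT evaluability is undefined. SAP 7.5 keeps all data from subjects who leave early, so dosed, replaced subjects remain. SAP 7.5.3 lists DLT-associated events and SAP 7.5.1 lists dosing by subject, which lets a reader rebuild most of the run-in count by hand.

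**Precision.** Clopper-Pearson 95% intervals are 0.4–64.1% for 1/6 and 4.3–77.7% for 2/6. The SAP plans no interval for DLT incidence.

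**The case against.** The strongest defence is that the SAP follows the protocol. Protocol 12.1.8 puts DLTs on the Safety Analysis Set, and protocol 12.1.2.1.1 words the endpoint for the whole study, so a whole-study DLT incidence is a legitimate planned quantity. That stands, and it is a reason to keep the existing row. It does not supply the run-in figure named in the synopsis, and it places the gap in protocol 12.1.2.3 as well as in the SAP.

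Three further points also stand. The Safety Review Committee decides on the first six subjects, not on this table. The listings largely allow reconstruction, so the run-in result is not beyond checking; it is only absent from every planned table. And if nobody was replaced and nobody was enrolled after the run-in, the two denominators coincide and the effect is nil.

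A reader might go further and infer that everyone enrolled after the run-in is scored as having no DLT, so that the table necessarily dilutes the run-in rate to 5% or 10%. The documents do not support that. Those figures need zero DLTs among later subjects, while protocol 10.4 and 10.5.1 leave room for later DLTs to be counted. For later subjects, the accurate word is mixing.

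**Conclusion.** The point holds as a gap in reporting. DLT incidence is planned only on the Safety Analysis Set, no DLT-evaluable set exists, and no planned table gives the figure that corresponds to the 1-of-6 rule.

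The one effect with a certain direction comes from dosed, replaced run-in subjects, who scale the run-in proportion by 6/(6+r). For two DLTs the fall from 33.3% is to between 28.6% and 22.2% for r = 1 to 3, and there is none if r = 0. This assumes that six evaluable subjects were reached and that no subject with a DLT was replaced. Pooling with later subjects is a separate matter of uncertain sign: 2/6 becomes anything from 10% (no later DLT) to 35% (five), if 14 later subjects are assumed.

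The actual size cannot be known from the documents. No dosing decision depends on it. The change is still worth making before database lock, because the denominator of a primary safety figure should not be left to the programmer.

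**What to change.** - **SAP 7.2:** add a DLT-Evaluable Set of run-in subjects that excludes exactly those replaced under protocol 9.1.3 and keeps every subject with a DLT. It should not be wider than that rule. Section 9.1.3 replaces early stoppers only for progression or refusal, so excluding everyone who left before Day 21 would also remove subjects whom the protocol does not replace.
- **SAP 7.5.2:** report DLT n/N with a Clopper-Pearson 95% interval on that set, by dose regimen. Keep the Safety Analysis Set row, labelled as supportive, and state whether DLTs in subjects enrolled after the run-in are counted in it.
- **SAP 7.7:** record the added set as a change from protocol 12.1.2.3 and 12.1.8.

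The cost is one population flag and one small table. The run-in DLT rate may look less favourable than the pooled one, and its interval will be wide (0.4–64.1% for 1/6), which is an honest picture of what six subjects can show.

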7.6 Determination of Sample Size

The sample size of 20 subjects is considered adequate on clinical grounds to judge the safety of the combination therapy and obtain an initial estimate of its clinical efficacy.

The sample size of 6 subjects for the safety run-in portion is considered adequate to make an initial assessment of the safety of the combination therapy prior to enrolling a full 20-subject cohort.

7.7 Changes in the Conduct of the Study or Planned Analyses

The analyses outlined in this SAP include deviations from the protocol as outlined below.

- Efficacy analyses will not be summarized due to early discontinuation of the study and a limited amount of available efficacy data.

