Pharmacokinetic (PK) Analysis Set: All subjects who receive at least one dose of FLX475 in combination with ipilimumab, and have measurable plasma concentrations of FLX475.

Pharmacodynamic (PD) Analysis Set: All subjects who receive at least one dose of investigational product and have sufficient PD data to derive at least one PD measurement.

Analysis Methods

Evaluation of data will consist primarily of descriptive statistics, summary displays, and data listings. Efficacy and safety data will be presented by treatment and tumor type. The number of subjects enrolled and discontinued from the study (by reason) will be presented. Demographic and baseline characteristics will be summarized for both the Safety Analysis Set and Efficacy Evaluable Set.

The incidence of adverse events will be presented by system organ class, preferred term, and maximum toxicity grade for subjects. Separate summaries will be provided for all adverse events, drug-related adverse events, serious adverse events, and adverse events leading to discontinuation of study treatment. Hematology and clinical chemistry data will be summarized by worst-case toxicity grade shift relative to baseline. Deaths will be listed by primary cause and date relative to last dose of study medication.

Efficacy endpoints will be summarized using descriptive statistics, including mean, standard deviation, median, and range for continuous endpoints and frequency tables for categorical data. Estimates of ORR and other response proportions will be presented together with 95%

confidence intervals calculated using the Clopper-Pearson method. Kaplan-Meier estimation will be used for the analysis of time-to-event endpoints, including DOR, PFS, and OS.

Rationale for Sample Size

The sample size of 20 subjects is considered adequate on clinical grounds to judge the safety of the combination therapy and obtain an initial estimate of its clinical efficacy. The ORR for the combination therapy is hypothesized to exceed the value observed with ipilimumab monotherapy (10–15%, [Long et al., 2017](#)).

To be considered evaluable, subjects must meet criteria for the Efficacy Evaluable Set (defined above), be evaluable as per RECIST v1.1 at 9 weeks, and should have no major protocol deviations. Evaluability for tumor response will be based on the following:

- Subjects who remain on study until the first evaluation (at 9 weeks) and are evaluated.

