12.1.8.3 Laboratory Values

Laboratory results will be summarized using Système International units, as appropriate. For all quantitative parameters listed in [Section 11.5.5](#), the actual value and the change from baseline to each postbaseline visit and to the end of treatment (defined as the last on-treatment value) will be summarized by visit using descriptive statistics. Laboratory parameters will be categorized according to CTCAE v5.0 grade, and shifts from baseline CTCAE grade to worst post-baseline grade will be summarized using shift tables. Percentages will be based on the number of subjects with baseline and at least 1 post-baseline assessment.

Common Terminology Criteria for Adverse Events v5.0 will be used to identify subjects with treatment-emergent markedly abnormal laboratory values (TEMAV). A more detailed definition of TEMA V will be specified in the SAP. A summary of TEMA Vs will be presented by treatment arm.

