4 INTRODUCTION

The purpose of this statistical analysis plan (SAP) is to provide comprehensive and detailed descriptions of the methods and presentation of data analyses proposed for RAPT Therapeutics, Inc. Protocol FLX475-03 (Phase 2 Study of FLX475 in Combination with Ipilimumab in Advanced Melanoma). Descriptions of planned analyses are provided in order to avoid post hoc decisions that may affect the interpretation of the statistical analysis. The statistical methods applied in the design and planned analyses of this study are consistent with the International Council for Harmonisation (ICH) guideline *Statistical Principles for Clinical Trials* (E9) (1998).

This SAP will be finalized prior to data analysis and before database lock to provide full details to be presented in the clinical study report (CSR). Any changes between the statistical methods provided in the clinical study protocol and this SAP will be explained herein; any changes or deviations from this SAP relative to the final analysis will be fully documented in the CSR. Minor changes or deviations from the templates for tables, figures, and listings need not be documented in the CSR.

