- TEAEs leading to discontinuation of study treatment (overall and FLX475 or ipilimumab related);
- Serious TEAEs (overall and any serious FLX475 or ipilimumab related);

In addition, a summary will be provided for the number and percentage of subjects with TEAEs by the highest NCI CTCAE grade. For this summary, subjects with multiple adverse events will be counted only once by the highest NCI CTCAE grade within an SOC and preferred term.

7.5.3 *Deaths, Other Serious Adverse Events, and Other Significant Adverse Events*

All deaths during the study, including the post treatment follow-up period, will be listed by subject, to include the primary cause of death. Serious AEs, AEs of clinical interest, and AEs associated with DLT will be provided in separate subject data listings.

7.5.4 *Clinical Laboratory Evaluation*

Hematology and chemistry parameters will be summarized by visit for the Safety Analysis Set. Only scheduled visit values will be included in this summary.

All clinical laboratory data will be listed by subject. Values outside the normal ranges will be flagged and toxicity grades will be displayed for relevant parameters. Hematology and chemistry measurements identified as abnormal (i.e., outside the normal range) will also be listed separately by subject, laboratory test, and unit.

7.5.5 *Vital Signs, Physical Findings, and Other Observations Related to Safety*

7.5.5.1 *Vital Signs*

Vital signs measurements include heart rate, respiratory rate, temperature, systolic blood pressure, and diastolic blood pressure. Vital signs will be listed by subject.

7.5.5.2 *12-Lead Electrocardiogram*

ECG measurements include heart rate, PR interval, RR interval, QRS interval, QT interval, QTc intervals. The number and percentage of subjects with elevated QTcF values (≥ 450 msec, > 480 msec, and > 500 msec) at baseline and any time post baseline will be presented. In addition, the number and percentage of subjects with QTcF values that increase by > 30 msec and > 60 msec from baseline to any time post baseline will be presented. ECG data will also be listed by subject.

7.5.5.3 *Physical Examination*

Results of the physical examination will be presented in subject data listings.

7.5.5.4 *Prior and Concomitant Medications*

Prior and concomitant medications will be coded using the World Health Organization Drug Dictionary (WHODD). Prior medications include medications that were stopped

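### SAP section 7.7 declares efficacy as the only departure from the protocol, but eight protocol-required safety outputs, including worst-grade laboratory shifts, TEMAV and dose reduction or interruption counts, are also dropped

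*SAP*

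**What the plan says.** The SAP commits itself to full disclosure of changes. Its introduction (section 4) says "Any changes between the statistical methods provided in the clinical study protocol and this SAP will be explained herein". Section 7.7 then opens with "The analyses outlined in this SAP include deviations from the protocol as outlined below" and contains a single bullet, on efficacy.

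The protocol's safety plan is more extensive than the one in SAP section 7.5. For laboratory data, protocol section 12.1.8.3 says that "shifts from baseline CTCAE grade to worst post-baseline grade will be summarized using shift tables", and the synopsis repeats it: "Hematology and clinical chemistry data will be summarized by worst-case toxicity grade shift relative to baseline". The same protocol section calls for a summary of treatment-emergent markedly abnormal laboratory values (TEMAV) and leaves the definition to the SAP: "A more detailed definition of TEMA V will be specified in the SAP". Sections 12.1.2.1.1, 12.1.8, 12.1.8.1, 12.1.8.4 and 12.1.8.5 add further summaries of dose modification, vital signs, ECGs and time to treatment failure.

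For laboratory data, SAP section 7.5.4 plans one by-visit summary, with the restriction "Only scheduled visit values will be included in this summary", and listings. SAP section 7.1.2 foresees using unscheduled data for the "determination of worst post-baseline value", but no laboratory table in the SAP uses such a value.

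**The concern.** Once efficacy is dropped, safety and tolerability is the only primary objective that the SAP still summarises. Cutting the safety package without saying so therefore affects the main content of the study report.

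The laboratory gap is the most concrete. An abnormality that leads to intervention, or to withholding or withdrawal of study treatment, should be recorded as an adverse event under protocol section 11.5.1 and would then reach the TEAE tables. The same section leaves the classification of an isolated abnormality to the investigator's judgment, and footnote e to protocol Table 2 mentions asymptomatic amylase or lipase elevations of Grade 3 or higher judged not clinically relevant. Such a value, if not reported as an adverse event, appears in no graded table. Its grade would be visible only in listings. If it was measured at a scheduled visit, it could also appear as an ungraded minimum or maximum.

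Dose reductions and interruptions are a direct measure of tolerability, yet no table counts them. A reader who relies on section 7.7 would conclude that the protocol's safety analyses were carried out unchanged.

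**Working it through.** The documents give no figure to reproduce here. The check compares the protocol's safety outputs with SAP sections 7.5.1 to 7.5.5, and then with section 7.7.

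| # | Protocol output | Protocol section | What the SAP plans | Declared in SAP 7.7? |
|---|---|---|---|---|
| 1 | Laboratory shift tables, baseline to worst CTCAE grade | Synopsis; 12.1.8.3 | By-visit summary of scheduled values, and listings (7.5.4) | No |
| 2 | TEMAV summary, definition left to the SAP | 12.1.8.3 | Not mentioned | No |
| 3 | Number of subjects with dose reduction or interruption | 12.1.8.1 | Duration, total dose, number of infusions, administration listing (7.5.1) | No |
| 4 | Adverse events leading to reduction or interruption of either drug | 12.1.8 | Events leading to discontinuation only (7.5.2) | No |
| 5 | Vital signs by visit, with change from baseline | 12.1.8.4 | Listing (7.5.5.1) | No |
| 6 | ECG-finding shift tables | 12.1.8.5 | None (7.5.5.2) | No |
| 7 | ECG parameters by visit, with change from baseline | 12.1.8.5 | QTcF threshold and increase counts, and listing (7.5.5.2) | No |
| 8 | Time to treatment failure due to toxicity | Synopsis; 12.1.2.1.1 | Not mentioned | No |

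Result: of these 8, 0 are planned and 0 are declared.

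Two further items have the same status. The table of prior and concomitant medications (protocol 12.1.5) becomes listings only (SAP 7.5.5.4). Treatment-related TEAEs by maximum grade (protocol 12.1.8.2) are not planned, because the SAP's highest-grade table covers all TEAEs without a related subset. Adding both gives 8 + 2 = 10.

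**Can exposure totals replace the missing counts?** SAP section 7.5.1 defines duration as last dose date minus first dose date plus one, and also reports total dose. Assume a 63-day course and use dose levels from SAP Table 2, purely as arithmetic:

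- Full dosing: 63 × 100 mg = 6,300 mg.
- Course A, a 21-day gap in mid-course for any reason: (63 − 21) × 100 mg = 42 × 100 mg = 4,200 mg, duration 63 days.
- Course B, 21 days at 100 mg followed by 42 days at 50 mg: 2,100 mg + 2,100 mg = 4,200 mg, duration 63 days.

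Both courses show 63 days and 4,200 mg, which is 4,200 / 6,300 = 67% of full dosing. The planned summary figures cannot separate a dose reduction for toxicity from a gap in dosing.

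**The case against.** The strongest reply is proportionality. The study stopped early, the protocol leaves output detail to the SAP (section 12.1), and with few subjects listings may be enough. The SAP still plans summaries of DLTs, all, related, Grade 3 or higher, serious and Grade 5 TEAEs, discontinuations, TEAEs by highest grade, and QTcF outliers at any time post baseline. It displays toxicity grades in the laboratory listings and lists abnormal hematology and chemistry values separately. This is a fair description, and a smaller package may well be defensible. But the SAP gives early discontinuation as its reason for efficacy only. Leaving detail to the SAP also does not cover removing an output without explanation, least of all TEMAV, whose definition was assigned to the SAP.

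Four narrower points deserve an answer:

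- The count depends on grouping. Items 3 and 4 overlap, and the items were listed because they are missing, so 0 of 8 is not a rate of omission across all safety outputs. The total stays at about eight to ten under reasonable groupings.
- The dose example is simplified. Protocol section 10.5.1 describes an interruption before a reduced dose, and the by-subject administration listing would distinguish the two courses. The example shows only that the totals are ambiguous.
- Adverse event listings might record the action taken with study drug, so the administration listing may not be the only place where dose modifications appear. The documents do not settle this.
- Footnote e to Table 2 concerns continuing treatment, not adverse event reporting. The gap rests on the judgment rule in protocol section 11.5.1; the footnote only illustrates the kind of value affected.

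A by-visit laboratory table restricted to scheduled values is a normal convention. The defect is that no worst-value table accompanies it.

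**Conclusion.** The concern holds. Eight protocol safety outputs are missing from SAP section 7.5, ten if the medication table and related TEAEs by maximum grade are included. Section 7.7 declares none of them, so its statement of deviations is incomplete and the commitment in section 4 is not met. The conclusion rests on comparing the two texts and does not depend on the dose illustration or on the exact count. Its practical weight is moderate: the underlying data would still appear in listings and the main adverse event tables are kept, but the SAP as written drops required summaries for the only primary objective still being summarised. The number of subjects treated is not given, so how much the missing tables would add cannot be judged from these documents.

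**What to change.** Either restore the outputs or declare their removal.

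- **SAP 7.5.4:** add a shift table from baseline to worst post-baseline CTCAE grade using scheduled and unscheduled values, in line with section 7.1.2. Define TEMAV and summarise it.
- **SAP 7.5.1 and 7.5.2:** add the number and percentage of subjects with interruption or reduction, separately for FLX475 and ipilimumab, and the TEAEs leading to each.
- **Remaining items:** restore the vital-sign, ECG-finding shift, by-visit ECG, time-to-treatment-failure and medication tables, and add related TEAEs by maximum grade.
- **SAP 7.7:** for any output not restored, list it and give the reason.

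The cost is a few standard tables from data already collected, or a short list of justified omissions. No new data are needed.
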